10.2.2 Clinical response assessment

The investigator will evaluate clinical response to treatment on Day 4(8) of the study (at Visit 2, switch from intravenous to oral therapy), within 1-2 days (Visit 3, end of treatment) and within 7-9 days (Visit 4, test of cure) after the last dose. Criteria for evaluation of clinical response to the therapy are presented in Table 10-1.

Table 10-1 Criteria for evaluation of clinical response

Category	Criteria
Clinical success	 All signs and symptoms of pneumonia presented at Visit 1 (Day 1) are resolved (i.g., resolution of fever, absence of intoxication, purulent sputum, and respiratory insufficiency) or improved with no worsening or appearance of new signs and symptoms of pneumonia. There is no requirement for additional antibiotic therapy. Chest roentgenograms (CT scans) are cured or improved (only for TOC visit).
Clinical failure	 Persistence or worsening in signs and symptoms of the acute process with either failure to show improvement in the clinical findings, initial improvement in signs and symptoms followed by clinically significant worsening before the assessment. Additional antimicrobial therapy required.

CONFIDENTIAL Page 53 of 88

	 Progression (worsening) of chest roentgenogram (CT scans) abnormalities or unchanged chest roentgenogram features (only for TOC visit).
	 Death because of pneumonia.
Indeterminate	• No evaluation possible: the patient was lost to follow-up, or died
	because of noninfectious-related reasons or infection other than
	pneumonia (as judged by the investigator).

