12 STATISTICAL METHODS

12.1 Analysis populations

The following populations will be identified for the statistical analyses:

- Randomized Population (RP): All subjects who were screened and randomized
- Intent-to-Treat Population (ITT): All subjects in the RT population who received at least one complete dose of the drug (Nemonoxacin or Tavanic[®])
- Modified Intent-to-Treat (mITT): Subjects in the ITT population who met the minimal disease criteria (inclusion criteria 3 and 4), and was evaluated for clinical efficacy at least once
- Clinically Evaluable (CE): Per-Protocol subjects in the mITT population (i.e. patients without protocol violations and without a clinical response of "Indeterminate" in the mITT population)
- Bacteriological mITT (b-mITT): Subjects in the mITT population whose bacterial culture yielded at least one baseline bacterial isolate
- Bacteriologically Evaluable (BE): patients in the CE population who had at least one baseline bacterial isolate
- Safety Population (SP): All subjects who received at least one complete dose of the study drug (Nemonoxacin or Tavanic®) and underwent at least one safety evaluation would be included in this data population for safety analysis
- Pharmacokinetic population (PK-C): All subjects who were included in PK study and who had at least 1 measured concentration value.

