12.6.2 Primary efficacy analysis

The percentage and the number of patients with different categories of clinical response ("clinical success", "clinical failure", "indeterminate") will be summarized by treatment group in mITT and CE populations for Visit 2 (switch to oral therapy), Visit 3 and Visit 4.

The percentage of patients with clinical success (as judged by the investigator) at the test of cure Visit 4 is defined as primary endpoint variable.

In regards to efficacy for CAP, non-inferiority of Nemonoxacin compared to Tavanic[®] will be evaluated for clinical response by using a one-sided 95% confidence interval for the difference in the primary efficacy endpoint (investigational drug minus comparator). Non-inferiority of Nemonoxacin will be stated if the lower boundary of the estimated one-sided 95% confidence interval for the difference in the clinical success rate of Nemonoxacin and Tavanic[®] is above -15% the Farrington-Manning test.

CONFIDENTIAL Page 65 of 88

The primary analysis will be performed in the mITT population.

If non-inferiority is shown, a test on superiority will be performed in addition using the two-sided 95% confidence interval. The test on superiority is significant, if the lower two-sided 95% confidence interval limit is above "0".

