12.6.3 Secondary efficacy analyses

As a supportive analysis, the primary efficacy endpoint will be analyzed in the CE population using the same method as that used for the primary efficacy analysis.

For secondary efficacy analyses, the clinical success rates of the patients in the mITT and CE populations at Visit 2 (switch to oral therapy) and Visit 3 as well as the number (proportion) of patients who needed other antibiotic treatment (treatment failure) will be analyzed using a two-sided 95% confidence interval (equality test) calculated based on the same statistical test as for the primary analysis.

Additionally, the results of statistical comparison of the clinical success rates using the logistic regression will also be provided.

Time to switch therapy from i.v. to oral therapy will be evaluated using the Kaplan – Meier survival analysis method and compared by log-rank test between treatment groups. The Kaplan-Meier curves will be presented graphically.

Microbiological efficacy endpoints will include microbiological success rates evaluated per each patient and by identified pathogens in b-mITT and BE.

The percentage and the number of patients with microbiological success and failure will be summarized by visit and treatment group. Microbiological success is defined as the assessments of eradication and presumed eradication. Other results of assessments (excluding unevaluable) will be regarded as microbiological failure. The difference between microbiological success rates and its CI will be calculated using the same method as that used for the secondary efficacy endpoints.

The percentage and number of the baseline-identified strains (sputum and blood culture) with microbiological success and failure will be summarized by visit and treatment group. The frequency of each category and sample source (sputum and blood culture) will be presented separately and by treatment group. Microbiological data by identified pathogens will be analyzed descriptively.

Microbiological efficacy evaluation

Based on the results of culture (bacteriological) study the microbiological response will be assessed. Microbiological response is defined as:

- 1. Eradication (admission pathogen[s] is absent),
- 2. Presumed eradication (if no material available for culture because of clinical success)
- 3. Persistence (admission pathogen[s] is present),
- 4. Presumed persistence (no material available for culture for patients with clinical failure),

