- 5. Unevaluable (assessment is not possible because the patient was lost to follow-up after the treatment or posttherapy culture was not obtained).

CONFIDENTIAL Page 66 of 88

6. Superinfection is defined as the appearance of a new pathogen in patients with clinical failure.

The eradicated and presumed eradicated microbiological responses will be combined and classified as microbiological success. Other results of assessments (excluding unevaluable) will be regarded as microbiological failure.

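### On the natural reading of 12.6.3, Unevaluable patients leave the b-mITT microbiological success rate while lost patients stay in mITT as clinical non-successes, so the b-mITT difference does not reflect unequal loss

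*Combined protocol and SAP*

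**What the plan says.** **Microbiological response.** Section 12.1 defines b-mITT as "Subjects in the mITT population whose bacterial culture yielded at least one baseline bacterial isolate"; no later culture is required. Section 12.6.3 names the endpoints and sets: "Microbiological efficacy endpoints will include microbiological success rates evaluated per each patient and by identified pathogens in b-mITT and BE". Eradication and presumed eradication are successes. For the rest, "Other results of assessments (excluding unevaluable) will be regarded as microbiological failure"; the synopsis has the same rule. Unevaluable means that "assessment is not possible because the patient was lost to follow-up after the treatment or posttherapy culture was not obtained". Patients with no material to culture are classed from clinical outcome, as presumed eradication after clinical success and presumed persistence after clinical failure. The per-patient summary by visit and arm lists success and failure only. The difference and its interval use the method for secondary endpoints, a two-sided 95% interval.

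**Clinical response.** Table 10-1 (10.2.2) defines Indeterminate: "No evaluation possible: the patient was lost to follow-up, or died" of a cause other than the pneumonia. Under 12.1 a patient enters mITT if the minimal disease criteria are met "and was evaluated for clinical efficacy at least once". CE is the set that requires patients to be "without a clinical response of 'Indeterminate' in the mITT population". In 12.6.2 the three response categories, Indeterminate among them, "will be summarized by treatment group in mITT and CE populations".

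**Missing data.** Section 12.5 leaves the general rules to a Statistical Analysis Plan whose text is not in the document.

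**The concern.** A patient with a baseline isolate who has one clinical evaluation and is then lost belongs to both mITT and b-mITT. At Visit 4 that patient is Indeterminate clinically and Unevaluable microbiologically. In the clinical rate the patient counts against the arm; in the microbiological rate the patient appears to vanish.

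If one arm loses more patients, the clinical difference registers it and the b-mITT difference does not. BE draws on CE, which already removes Indeterminate patients, so comparing b-mITT with BE would say little about the effect of loss, although showing that effect is one reason to report both sets. Microbiological efficacy is a stated secondary objective (4.2) with a planned between-arm interval, so the denominator should be fixed before the loss pattern is known.

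**Working it through.** **1. The rules side by side**

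| | Clinical, mITT | Microbiological, b-mITT |
|---|---|---|
| Category for a lost patient | Indeterminate | Unevaluable |
| Removed from the set? | No, only from CE | No |
| In the planned response summary? | Yes, a third category | No, success and failure only |
| Effect on the success rate (natural reading) | In the denominator, non-success | Out of the denominator |

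Neither denominator is written out; the last row is inferred from the rows above it.

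**2. Inputs**
- From 12.10: 171 randomized per arm, 80% eligible for mITT, 82% clinical success. The step 171 × 0.80 = 136.8, about 137 per arm, is correct. (The stated margin, alpha and power need only 82 to 84 per arm. That is a separate matter; 137 serves here only as the expected mITT size.)
- Assumed, because the plan gives no figure: 30% of mITT patients have an isolate, so 0.30 × 137 = 41 per arm (range 27 to 68); success among evaluable patients is 82% to 85%, equal in both arms; the unevaluable shares are as shown below.

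**3. Formula**

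Let p be success among evaluable patients and d the unevaluable share, with T for nemonoxacin and C for Tavanic. Dropping Unevaluable gives a rate of p; keeping it as non-success gives p(1 − d). With equal p, the difference T − C moves by −p(dT − dC).

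- p = 82%, 10% v 5%: −0.82 × 0.05 = −4.1 points
- p = 82%, 15% v 5%: −0.82 × 0.10 = −8.2 points
- p = 85%, 4 v 1 of 41: −0.85 × 3/41 = −6.2 points
- p = 85%, 6 v 2 of 41: −0.85 × 4/41 = −8.3 points
- equal loss: 0

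For 15% v 5%, varying p from 70% to 90% gives −7.0 to −9.0. At 20% v 5% and p = 82% the shift is −12.3. If Tavanic loses more patients, the sign reverses. For scale, the standard error at 41 per arm and p = 85% is √(2 × 0.85 × 0.15/41) = 7.9 points.

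**4. Whole-number examples, about 15% v 5% unevaluable, p about 82%** (two-sided 95% Farrington-Manning intervals)

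| Per arm | Unevaluable | Dropped | Kept as non-success |
|---|---|---|---|
| 27 | 4 v 1 | 19/23 v 21/26: +1.8 (−21.2 to +23.9) | 19/27 v 21/27: −7.4 (−30.4 to +16.1) |
| 41 | 6 v 2 | 29/35 v 32/39: +0.8 (−17.4 to +18.4) | 29/41 v 32/41: −7.3 (−26.0 to +11.7) |
| 68 | 10 v 3 | 48/58 v 53/65: +1.2 (−12.8 to +14.8) | 48/68 v 53/68: −7.4 (−21.9 to +7.4) |

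A similar loss pattern across all 137 mITT patients per arm (21 v 7 Indeterminate) gives a clinical difference of 95/137 − 107/137 = −8.8 points. The clinical analysis shows the loss; the b-mITT analysis, on the natural reading, does not.

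**5. Overlap of categories**

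Unevaluable includes patients with no post-therapy culture, whatever their clinical outcome. Section 10.2.3 takes sputum only where the investigator finds it necessary and possible, and omits repeat blood cultures after a negative Visit 1 culture. A cured patient with nothing to culture therefore fits both presumed eradication and Unevaluable. Without an order of precedence, counting every Unevaluable patient as non-success could score cured patients as microbiological non-successes.

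**The case against.** The strongest reply is that the sentence in 12.6.3 defines failure, not the denominator of the success rate, and that 12.5 defers missing data to a plan not seen here. The first half stands: exclusion is an inference. It is still the natural one, because the rule is specific to this category, recurs in the synopsis, and is paired with a summary of successes and failures only. A general deferral does not override it. If the intent was otherwise, one sentence stating the denominator is still needed.

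Several stronger conclusions are tempting, and the documents do not support them:
- *It is a complete-case analysis.* It is not. The presumed categories keep many patients without cultures, and needing other antibiotics makes a patient a clinical failure, hence presumed persistence when there is no material. Only the unevaluable remainder is dropped.
- *The plan hides unequal loss.* Indeterminate is tabulated by arm and visit in mITT, and 12.6.3 plans category frequencies by arm. That plan sits in the strain-level paragraph, however, and does not require Unevaluable per patient and visit; nor would a count alter the estimate.
- *b-mITT and BE are interchangeable.* BE also carries CE's exclusions for ineligibility, poor compliance, short treatment, wrong treatment and major deviations.
- *A non-inferiority claim is biased.* The 15% margin belongs to the primary clinical endpoint.

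It is also fair that loss may be small before Visit 4: patients stay in hospital during treatment (6.1), and withdrawal triggers an early-termination visit with clinical assessment and cultures (7.3, 9.2.3). Patients lost before any clinical evaluation are outside both sets.

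**Conclusion.** The point holds as a mismatch between two rules, on the natural reading of 12.6.3. The b-mITT rate leaves out the Unevaluable remainder, while mITT keeps the lost patient as a non-success, so the b-mITT difference does not reflect unequal loss.

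Under the assumptions above the effect is roughly 4 to 8 points, or about half to one standard error; it is zero if loss is equal. These sizes rest wholly on assumed isolate, success and loss rates. In the 41-per-arm example the interval includes zero under either rule, and applying the presumed categories first would shrink the Unevaluable group and the shift with it.

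A reader might infer that the trial's main result is at risk. It is not: this is a secondary endpoint with a two-sided interval and no margin. The change is worth making because the rule is incomplete, the repair is cheap, and the denominator should not be chosen after the loss pattern is seen.

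**What to change.** Amend 12.6.3 and the synopsis before database close-out:

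1. **Precedence.** Where there is no culture material at a visit but a clinical success or failure is recorded for it, assign presumed eradication or presumed persistence first. Reserve Unevaluable for patients with neither a culture nor a clinical success or failure at that visit.
2. **Denominator.** In b-mITT, divide by all b-mITT patients and count Unevaluable as non-success, matching Indeterminate in mITT. Exclude Unevaluable only in BE. Keep the evaluable-only b-mITT rate as a pre-specified sensitivity analysis.
3. **Reporting.** Show Unevaluable counts per patient by arm and visit.

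The order matters: step 2 without step 1 could penalise cured patients who have nothing to culture. The cost is a few sentences, one extra table and one sensitivity analysis, with no new data. The downside is that the b-mITT success rates become somewhat lower in both arms.

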10.2.3 Bacteriological study

Sputum sample for the culture (bacteriological) study for isolation of pathogens will be collected before the initiation of therapy on Day 1 of the study (at Visit 1, during screening procedures) and before the first oral dose of IMP on Day 4(8) of the study (Visit 2, switch to oral therapy), within 1-2 days (Visit 3) and within 7-9 days (Visit 4) after the last dose. This procedure will be performed only if it will be necessary and possible (according to the judgment of the investigator) to collect the sputum from patient (deep expectorated / broncho-alveolar lavage, etc.).

Blood sample collection for bacteriological study will be done before the initiation of the therapy on Day 1 (at Visit 1, screening procedures) and before dosing on Day 4(8) of the study (at Visit 2, switch to oral therapy), within 1-2 days (Visit 3) and within 7-9 days (Visit 4) after the last dose. However blood sampling at Visit 2, 3 and 4 should not be conducted if no bacterial growth has been detected by blood cultures of samples withdrawn at Visit 1.

The results of bacteriological study will be documented in eCRF.

Causative pathogens of CAP listed below will be determined in sputum/blood samples:

- S. pneumoniae
- H. influenzae
- S. aureus
- K. pneumoniae
- P. aeruginosa
- Other.

Bacteriological study will be performed in the local laboratory of investigational site. After isolation of pathogens culture from some previously defined laboratories can be sent to a central laboratory for additional investigations by a decision of the Sponsor. Detailed information about central laboratory, conditions of culture transportation are provided in appropriate Manual. The Sponsor will use these isolates to perform additional culture (bacteriological) studies, including drug sensitivity test, etc..

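### The microbiological response categories in 12.6.3 overlap and have no stated order, so the same patient can be a success, a failure or left out depending on how the text is read

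*Combined protocol and SAP*

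**What the plan says.** Section 12.6.3 lists six microbiological responses. Four matter here, besides plain Eradication (admission pathogen absent) and Persistence (admission pathogen present):

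- Presumed eradication applies "if no material available for culture because of clinical success".
- Its counterpart is worded "Presumed persistence (no material available for culture for patients with clinical failure").
- Unevaluable means "assessment is not possible because the patient was lost to follow-up after the treatment or posttherapy culture was not obtained". The clause at issue is its last, "posttherapy culture was not obtained".
- "Superinfection is defined as the appearance of a new pathogen in patients with clinical failure".

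For counting, "The eradicated and presumed eradicated microbiological responses will be combined and classified as microbiological success". Everything else except Unevaluable is a failure, so Superinfection and Presumed persistence are failures and Unevaluable is neither. No order of precedence is given.

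On sampling, 10.2.3 says of sputum collection: "This procedure will be performed only if it will be necessary and possible (according to the judgment of the investigator"). Table 9-1 and the visit descriptions in 9.2.2 to 9.2.4 instead schedule a sputum culture whenever the patient has sputum. Blood culture is not repeated after a negative Visit 1 culture.

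Microbiological efficacy is a secondary objective (4.2), assessed at Visits 2, 3 and 4 (5.1.2). Between-group differences with confidence intervals are planned, and success rates are evaluated in the b-mITT and BE populations (12.6.3).

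**The concern.** A response classification has to send every patient to exactly one box. Here some patients fit two boxes that count in opposite ways, or one that counts and one that does not. Two programmers working faithfully from 12.6.3 could produce different numerators and different denominators from the same data.

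The sampling rule adds a second problem. If the presence of material decides between a presumed category and Unevaluable, the investigator's decision to culture or not decides whether a clinical failure stays in the denominator. Dropping failures raises the success rate in whichever group it happens.

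Patients who need other antibiotics are particularly exposed. They are withdrawn under 7.3 and are clinical failures under Table 10-1, yet may have neither a culture nor a clinical assessment at Visit 4. Nothing in 12.6.3 says whether the earlier failure carries forward.

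**Working it through.** **Step 1: apply the definitions to each type of patient.**

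| Patient at a visit | Categories met | Counted as |
|---|---|---|
| Clinical failure, admission pathogen absent, new pathogen present | Eradication and Superinfection | success / failure |
| Clinical success, no material | Presumed eradication and, literally, Unevaluable | success / left out |
| Clinical failure, no material | Presumed persistence and, literally, Unevaluable | failure / left out |
| Clinical failure, sputum present but not cultured | Unevaluable only | left out |
| Visit 2, clinical response Indeterminate, no culture | none, read strictly | undefined |

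The first row arises because Eradication carries no condition on clinical response. The last arises because Unevaluable is worded for the period after treatment, whereas Visit 2 is on treatment.

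**Step 2: gap between the two readings of no material.** The plan gives no figure for this endpoint, so there is none to reproduce. The one input from the documents is S = 0.82, the clinical success rate assumed in 12.10. The rest are assumptions:

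- f = share of clinical successes without culture: 25, 50, 75 or 90%
- g = share of clinical failures without culture: 10, 25 or 50%
- eS, eF = eradication among cultured successes and failures: 100/30, 90/30 or 80/20%

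Reading A (presumed categories first, every uncultured patient taken to have no material): A = S·f + S(1-f)·eS + (1-S)(1-g)·eF.

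Reading B (Unevaluable first): B = [S(1-f)·eS + (1-S)(1-g)·eF] / [S(1-f) + (1-S)(1-g)].

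- Middle case, f = 75%, g = 25%, 90/30: A = 0.615 + 0.1845 + 0.0405 = 84.0%. B = 0.225/0.340 = 66.2%, keeping 34% of patients.
- f = 25%, g = 25%, 90/30: A = 0.205 + 0.5535 + 0.0405 = 79.9%. B = 0.594/0.750 = 79.2%. Gap 0.7 points.
- Lowest A minus B (f = 25%, g = 50%, 100/30): 84.7% - 91.1% = -6.4 points.
- Highest (f = 90%, g = 10%, 80/20): 83.6% - 40.2% = +43.4 points.

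By f, A minus B runs from -6.4 to +5.4 points at 25%, -2.7 to +14.0 at 50%, +6.1 to +27.6 at 75% and +21.3 to +43.4 at 90%.

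The treatment difference can move too. With 82% clinical success in both groups, g = 25%, 90/30, and f = 70% in one group against 80% in the other, it is 83.6% - 84.4% = -0.8 points under A and 68.7% - 62.9% = +5.8 points under B.

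**Step 3: uncultured failures, with presumed categories first.** If every uncultured failure had sputum, all of them leave the denominator and the rate becomes A/[1 - (1-S)g]. This is an upper limit. With f = 75% and 90/30:

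- g = 10%: 0.848/0.982 = 86.4%, up 1.6 points
- g = 25%: 0.840/0.955 = 88.0%, up 4.0 points
- g = 50%: 0.8265/0.910 = 90.8%, up 8.2 points

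**Step 4: Eradication against Superinfection.** The most that can switch under reading A is (1-S)(1-g)·eF, reached if every cultured failure who has cleared the admission pathogen has a new one. In the middle case this is 0.18 × 0.75 × 0.30 = 4.1 points. Across the assumptions it runs from 0.18 × 0.50 × 0.20 = 1.8 to 0.18 × 0.90 × 0.30 = 4.9 points.

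**The case against.** The strongest reply is that Unevaluable opens with the condition that assessment is not possible. The presumed categories are assessments made without a culture, so they should come first and Unevaluable should take what is left. Reading B would also leave both presumed categories empty, although the plan expressly counts presumed eradication as success. This stands: presumed-first is the natural reading, and the wide gap in Step 2 is what a literal implementation could produce, not a likely error. But the order is not written, and this reading does not resolve the superinfection conflict or the uncultured failures.

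The schedule calls for culture whenever sputum is present, so uncultured failures should be few. That too is fair, but 10.2.3 is looser and permits them.

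Two stronger inferences are tempting. One is that most responders fit two categories. The documents give neither the size of b-mITT nor the share without material. Improved patients count as successes and may still produce sputum, and patients with a positive baseline blood culture are sampled again. The other is that the rule favours one treatment. Investigators are blinded (8.6), and nothing suggests that sampling would differ by group. The unequal shares in Step 2 only show sensitivity.

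Finally, 12.5 and 12.9 defer missing-data rules and analysis detail to a separate SAP, whose text is not among the documents. It could set the order. The conflict, however, lies in the category definitions themselves.

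**Conclusion.** The point holds for three groups: clinical failures with a new pathogen and the admission pathogen gone; patients with no follow-up material, where the order is implied but not stated; and clinical failures with sputum that was not cultured, who are lost from the denominator even on the sensible reading. The first and third do not depend on how Unevaluable is ordered against the presumed categories.

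The size cannot be fixed from the documents. The range of about -6 to +43 points between readings rests entirely on assumed culture and eradication shares, and the gap nearly vanishes in one scenario with a quarter uncultured. On the natural reading, the ceilings are about 2 to 8 points for uncultured failures (with f = 75% and 90/30 eradication) and about 2 to 5 points for superinfection.

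This concerns a secondary endpoint with no stated non-inferiority margin, and the primary endpoint is untouched. It should still be settled before the SAP is final, because it decides who counts as a failure in a planned between-group comparison.

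**What to change.** Replace the list in 12.6.3 with one rule, applied in this order at each visit:

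1. New pathogen with clinical failure: Superinfection (failure).
2. Admission pathogen present: Persistence (failure).
3. Cultured and admission pathogen absent: Eradication (success).
4. No culture material, with clinical success: Presumed eradication (success).
5. No culture result for any reason, with clinical failure, including failures declared at an earlier visit and withdrawn for other antibiotics: Presumed persistence (failure).
6. Unevaluable only for the remainder: clinical response Indeterminate or missing without a culture, or clinical success with material available but not cultured.

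Step 4 stays limited to absent material, so that a success is not presumed merely because an available sample was not cultured. Reword the Unevaluable clause to match, without reference to the period after therapy, so that the rule also works at Visit 2.

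Report documented and presumed eradication in separate rows at patient level. Section 12.6.3 already presents the frequency of each category in its paragraph on baseline-identified strains, so this extends an existing table.

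The cost is wording in one section and one derivation. The downside is that slightly more responses are inferred from the clinical assessment, which the separate rows make visible.
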